14.3. Interim Safety Analysis

Based on the reported coronary perforation (0.37%), coronary dissection (7.7%) and transient ischaemic attack/ischaemic stroke (0.25-0.8%) rates in contemporary STEMI practice, in a 27-patient arm study, 1 coronary perforation, 1 significant coronary dissection and 1 transient ischaemic attack/ischaemic stroke may be expected by chance. If >2 (>10%) coronary perforation-related SADEs or >2 significant coronary dissection-related SADEs or >2 transient ischaemic attack-/ischaemic stroke-related SADEs occur in the investigational device arm this will be considered too high.

15. DATA MANAGEMENT

15.1. Source Data

Source documents are where data are first recorded, and from which participants' CRF data are obtained. These include, but are not limited to, hospital records (from which medical history and previous and concurrent medication may be summarised into the CRF), ECGs, radiographic and OCT images and correspondence. Access to relevant source data will be sought for members of the research team.

15.2. Data recording and Record Keeping

The study will comply with the Data Protection Act, which requires data to be anonymised as soon as it is practical to do so. This will be achieved by assigning participants a unique trial ID number that will be used in case record forms (CRFs), ECGs, radiographs, OCT and extracted thrombus images (pseudonymisation). A contact record form linking a participant's unique trial ID number with their personal identifiable data (name, hospital ID, personal address, emails or telephone numbers) will be used. This form will be kept in the code break folder, separate from other documents. This form is needed to perform the 6 months telephone follow-up and to ensure that in case of an emergency participants can be identified and contacted. The written informed consent form that contains personal data (name and signature) can not be anonymised, but will be kept in a separate folder to the pseudonymised data and stored securely at the Oxford University Hospitals NHS Foundation Trust and the Newcastle upon Tyne Hospitals NHS Foundation Trust.

Study data will be entered into the CRFs by members of the research team after reviewing source data and/or seeking information from the patient. This data will then be securely stored in an on-site location with restricted access and will only be accessible by study staff and authorised personnel. Pseudonymised data from non-Oxford sites can be transferred using appropriately encrypted means to Oxford University Hospitals NHS Foundation Trust. Source ECG data will be copied, identifiable data will be removed and subsequently labelled with the trial participant ID number. ECG's will be securely stored alongside the

Commented [GS(O9]: How will this be done?

Commented [RK10R9]: Hi [name], we typically use USB/hard drive/email but we don't want to restrict ourselves in the protocol in case of other suitable encrypted ways for data transfer.

Date and version No:22/04/2024 v4.0

participant's CRFs in an on-site location with restricted access and will only be accessible by study staff and authorised personnel. Radiographic and OCT imaging data will be de-identified using the unique trial participant ID number before downloading them on to encrypted electronic transfer media and transferred to be stored on to password protected NHS computers in an on-site location with restricted access. Pseudonymised data from non-Oxford sites can be transferred using appropriately encrypted means to Oxford University Hospitals NHS Foundation Trust. In Oxford, extracted thrombus imaging data will be stored in a de-identified format using the trial participant ID number on to password protected NHS computers in an on-site location with restricted access.

Personal data (contact record form) will be stored for 12 months after the study has ended, while pseudonymised research data generated by the study and any research documents with personal information, such as the consent forms, will be stored for 10 years. All study data and documents will be stored securely in an on-site location with restricted access. Study data will only be accessed by study staff and authorised personnel. After analysis is completed, data will be archived in a secure location with restricted access. After the specified data storage period elapses, the data custodian will agree a date for destruction and data will be destroyed confidentially at that time.

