11.3. Recruitment

RETRIEVE-AMI is a multi centre study recruiting at the John Radcliffe Hospital and the Newcastle upon Tyne Hospitals NHS Foundation Trust sites. Participants will be identified as they are being admitted for primary PCI. They will be approached by a research team member (a primary PCI operator who is also a member of the clinical care team) who will verbally assent them as explained in section 11.1.1.1. Upon assent, participant will be randomised to one of the three study arms, by a system based on sealed Envelope system. Consent will be completed at the post-emergency phase as described in section 11.1.1.3.

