11.4. Randomisation

Date and version No:22/04/2024 v4.0

Upon assent, participant will be randomised to one of the three study arms, by a system based on sealed envelopes. Randomization will take place in the cathlab once both inclusion and exclusion criteria are verified and assent provided.

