12.1.2. Aspiration thrombectomy and PCI (Arm 2)

Participants randomised to Arm 2 of the RETRIEVE AMI trial will have standard of care treatment with manual thrombectomy catheter and PCI. Participants will undergo PCI with devices and techniques driven by clinical decision making at the patient level and institutional level, and carried out in accordance with local guidelines.

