14.2. Analysis of Endpoints

In keeping with our usual practice, we will obtain expert statistical advice from the Centre for Statistics in Medicine (or equivalent) for each specific task. A flow diagram detailing number of participants screened and randomised will be provided. Analysis of the OCT-derived primary and secondary endpoints (including angiography-derived) will be conducted offline in a blinded fashion. Summary statistics, including means, medians, and variances, will be calculated at each time point and for each type of data and group (e.g. baseline characteristics, parameters derived from OCT, angiography-derived coronary physiology). The distribution of the levels will be described. For each parameter an analysis of variance will be carried out.

An analysis evaluating for a between group difference in pre-stent thrombus volume will first use an 1-way ANOVA with a 2-sided equality test to assess for an overall trend. Post-hoc analyses exploring the following hypotheses i) retriever thrombectomy (Arm 3) is different to no thrombus modification (arm 1) and ii) retriever thrombectomy (Arm 3) is different to aspiration thrombectomy (Arm 2) will be performed using the Dunnett test. Control of the Type I error at 5% two-sided significance level due to multiple testing will be achieved using Dunnett's method.³⁶ Missing data for the primary analysis will be dealt with complete case analysis if data missingness is <10% (<3 cases per group). If missingness is higher, multiple imputation will be performed instead. Major adverse cardiac and cerebrovascular events will be analysed using proportions statistical testing (Fisher's exact or χ^2 tests), yet they represent an exploratory analysis.

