Figure 4 Line diagram to illustrate the technique of using the thrombus retrieval device. (A) The vessel with thrombus is crossed with a workhorse wire that was pre-loaded with a Rebar micro-catheter. (B) Rebar micro-catheter was advanced beyond the thrombus. (C) The wire was removed; an appropriate sized Solitaire AB device was back loaded and advanced to the tip of the micro-catheter positioned beyond the thrombus. (D) The micro-catheter was pulled back maintaining the tip of the device at the same position. This makes the stent expand and trap the thrombus between its struts. (E) The stent device is then pulled back into the micro-catheter along with the trapped thrombus. (F) Once the device is completely within the micro-catheter the whole system is pulled out.

Schematic diagram of device operation¹⁵

Date and version No:22/04/2024 v4.0

27. APPENDIX D: Amendment history

Amendment No.	Protocol Version No.	Date issued	Author(s) of changes	Details of Changes made
1	V1.3	21/01/2022	[name] [name]	Sample size increase
2	V2	21/12/2022	[name] [name]	Changes in inclusion and exclusion criteria
3	v3.0	02/10/2023	[name] [name]	Inclusion of an additional site Extension of recruitment period

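### Section 14.2 analyses a two-site trial by arm only; a site factor would be a cheap, modest gain in precision, and its absence does not bias the contrasts

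*Combined protocol and SAP*

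**What the plan says.** - **Sites.** Section 11.3: "RETRIEVE-AMI is a multi centre study recruiting at the John Radcliffe Hospital and the Newcastle upon Tyne Hospitals NHS Foundation Trust sites". Appendix D records "Inclusion of an additional site" at protocol v3.0, dated 02/10/2023; the Synopsis gives a planned start of 01/03/2022.
- **Allocation.** The ratio is 1:1:1 (Section 9). Section 11.4: "Upon assent, participant will be randomised to one of the three study arms, by a system based on sealed envelopes". Neither 11.3 nor 11.4 says whether allocation is balanced by site.
- **Primary analysis.** Section 14.2 takes pre-stent thrombus volume and "will first use an 1-way ANOVA with a 2-sided equality test to assess for an overall trend". It then compares Arm 3 with Arm 1 and Arm 3 with Arm 2. On multiplicity: "Control of the Type I error at 5% two-sided significance level due to multiple testing will be achieved using Dunnett's method". Site appears nowhere in the model.
- **Image reading.** Section 14.2 says that analysis of the OCT and angiographic endpoints "will be conducted offline in a blinded fashion".
- **Second-site data.** Section 15.2, on record keeping: "Pseudonymised data from non-Oxford sites can be transferred using appropriately encrypted means to Oxford University Hospitals NHS Foundation Trust".

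**The concern.** Site is known for every patient at no cost. In a one-way ANOVA by arm, any site main effect on thrombus volume is counted as noise. Case mix is one possible source. Aspiration is another, because Section 11.6 leaves it to standard clinical practice. If the sites differ, the confidence intervals for both Arm 3 contrasts are wider than they need be.

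The form of the cost depends on allocation, which the plan leaves open:

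- If allocation is not balanced by site, chance differences in site mix between arms add to the sampling variance of each contrast. The test allows for this, so the only cost is precision.
- If allocation is balanced by site, the contrasts do not carry the site variation but the residual variance still does. The standard error is too large and the test is conservative.

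The trial is small, so precision available at almost no cost is worth having.

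**Working it through.** **Inputs from Section 14.1.** Control mean 9.6 mm³, SD 5.1 mm³, 33% reduction, 24 analysable patients per arm, two comparisons at two-sided 5%.

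**The plan's own figure.** The difference is δ = 0.33 × 9.6 = 3.168 mm³. The standard error of a contrast is 5.1 × √(2/24) = 1.472. The noncentrality is 3.168 / 1.472 = 2.152. Against a Dunnett critical value of 2.26 (69 df), power per contrast is about 46%. At unadjusted two-sided 5% it is 57.6%, and 80% would need 41 per arm. The stated 80% with 24 per arm does not reproduce. That is a separate matter; here 46% is only the base for comparison.

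**Assumed inputs (not in the documents).**
- *Newcastle share p.* With equal monthly recruitment over 36 months from March 2022, a start at v3.0 (October 2023) gives 17 site-months: 17 / (36 + 17) = 0.32. A start at the date of the current protocol (April 2024) gives about 10: 10 / (36 + 10) = 0.22.
- *Site gap g*, in within-site SDs: 0 to 1.
- *SD.* 5.1 is taken as the total SD, site variation included.

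**Formula.** Total variance = within-site variance × [1 + p(1 − p)g²]. A site term brings the error SD down to 5.1 / √[1 + p(1 − p)g²].

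- p = 0.32, g = 0.5: 5.1 / √1.0544 = 4.97; noncentrality 3.168 / (4.97 × √(2/24)) = 2.21; power about 48%.
- p = 0.32, g = 1: 5.1 / √1.2176 = 4.62; noncentrality 2.37; power about 55%.
- p = 0.22, g = 1: 5.1 / √1.1716 = 4.71; noncentrality 2.33; power about 53%.

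These closed-form values assume sites balanced across arms. With unbalanced sites the adjusted power is slightly lower, because the site effect has to be estimated.

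**Simulation.** Both models were fitted, with and without balance by site, at both shares. The table gives the range of the change in power per contrast when site is added.

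| Site gap (within-site SD) | Gap, mm³ | Change in power, points |
|---|---|---|
| 0 | 0 | 0 to about −0.5 |
| 0.25 | about 1.3 | about 0 to +1 |
| 0.5 | about 2.5 | +1 to +3 |
| 1 | about 4.6–4.7 | +6 to +10 |

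**Type I error of the arm-only analysis.** Familywise error is about 5% when allocation is not balanced by site. When it is balanced, it is about 4% at a gap of 0.5 SD and 2–3% at 1 SD. A simpler two-arm check with equal site shares gave 4.2% and 2.7%. In no case is it inflated.

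**If 5.1 is instead the within-site SD**, leaving site out multiplies the required sample size by 1 + p(1 − p)g². Over shares of 10–50% and gaps of 0.25–1 SD this runs from 1.006 to 1.25.

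**The case against.** The case for leaving the plan alone is substantial. An arm-only ANOVA is valid under random allocation. The trial is described as exploratory, has two sites, and plans to take statistical advice for each task. Gaps of 0.75 SD (about 3.6 mm³) or more exceed the whole target effect of 3.2 mm³, and nothing in the documents suggests a site difference that large. At 0.25 SD the gain is close to nil, and with no gap the term loses a little. All of this stands, and it limits the weight of the point.

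A reader might also infer stronger versions, which the documents do not support:

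- **Each site reads its own images.** The permissive wording in Section 15.2 is about secure transfer, and the margin comment beside it concerns the means of encryption. Section 15.4 concerns specialist processing. Section 14.2 already requires offline, blinded analysis. Local reading is conjecture.
- **Differences in PCI technique affect the endpoint.** Section 12.1 does leave PCI to "devices and techniques driven by clinical decision making at the patient level and institutional level". But the primary outcome is measured before stenting, and Section 11.6 puts PCI in Stage 4, after the pre-stent OCT. Aspiration practice could differ by site, but only in Arm 2. That would be partly an arm-by-site interaction, which an additive site term does not fully remove.
- **Site imbalance biases the contrast.** With 24 per arm, a 32% share and unrestricted allocation, about 16% of trials would show a gap of 20 points or more in Newcastle share between Arm 3 and a given control arm. At a 0.75 SD site difference this moves the estimate by 0.20 × 0.75 × 4.8 ≈ 0.7 mm³. That is chance variation already in the sampling variance, not an added error.
- **The eligibility changes make the sites differ.** Newcastle joined after the December 2022 criteria change, but Oxford recruits under the later criteria too. A site term would not separate early from late Oxford patients.

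**Conclusion.** The point holds as a modest matter of precision. Section 14.2 omits a factor known for every patient, and adding it costs almost nothing. The likely benefit is small: +1 to +3 power points at a 0.5 SD site gap, and +6 to +10 only if the gap reaches 1 SD, from a base of about 46%. If allocation is balanced by site, the term also removes the conservatism of the arm-only test.

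These figures rest on an assumed Newcastle share of 22–32%, an assumed range of site gaps, a total SD of 5.1 mm³ and 24 analysable patients per arm. The documents give neither the share nor the gap, so the actual gain cannot be fixed. They support no claim of bias, inflated error, local image reading or an effect of stenting technique on the primary outcome.

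**What to change.** In Section 14.2, fit the primary model for pre-stent thrombus volume with arm and site as fixed factors. Take both Arm 3 contrasts from that model, with the same Dunnett control at two-sided 5%. Make the change before any comparison by arm, so that the choice to adjust cannot depend on the results.

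The cost is a wording change and one degree of freedom (69 to 68 with 24 per arm), with about half a power point at most lost if the sites do not differ. It needs no extra patients, data or procedures, and it works whether or not the envelopes are balanced by site. The shortfall from the stated 80% power needs its own remedy.

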15.3. Access to Data

Direct access will be granted to authorised representatives from the Sponsor, host institution and the regulatory authorities to permit trial-related monitoring, audits and inspections.

15.4. Approval to share imaging data with third parties

De-identified research data including imaging data may be shared with the University of Oxford or other specialised centers in partnership with RETRIEVE-AMI, according to the availability of specialist analysis techniques that may not be available to the local research team. Data transfer and storage should follow the processes described in 15.2. Participants will be informed in the information leaflet and sign in the consent form (if they approve) that their pseudonymised images may in the future be sent to third parties

Date and version No:22/04/2024 v4.0

for specialist processing. It will be clearly stated that no identifying information will be sent with these imaging data.

16. QUALITY ASSURANCE PROCEDURES

16.1. Risk assessment

The trial will be conducted in accordance with the current approved protocol, ICH GCP, relevant regulations and standard operating procedures.

16.2. Monitoring

Regular monitoring will be performed by the sponsor according to ICH GCP. Data will be evaluated for compliance with the protocol and accuracy in relation to source documents. The monitors will verify that the clinical trial is conducted and data are generated, documented and reported in compliance with the protocol, GCP and the applicable regulatory requirements.

17. PROTOCOL DEVIATIONS

A trial related deviation is a departure from the ethically approved trial protocol or other trial document or process or from Good Clinical Practice (GCP) or any applicable regulatory requirements. Any deviations from the protocol will be documented in a protocol deviation form and filed in the trial master file.

All deviations will be reported to the MHRA.

18. SERIOUS BREACHES

A serious breach is defined as “A breach of GCP or the trial protocol which is likely to affect to a significant degree -

- (a) the safety or physical or mental integrity of the subjects of the trial; or
- (b) the scientific value of the trial”.

In the event that a serious breach is suspected the Sponsor must be contacted within 1 working day. In collaboration with the C.I., the serious breach will be reviewed by the Sponsor and, if appropriate, the Sponsor will report it to the REC committee, Regulatory authority and the NHS host organisation within seven calendar days.

19. ETHICAL AND REGULATORY CONSIDERATIONS

19.1. Declaration of Helsinki

The Investigator will ensure that this trial is conducted in accordance with the principles of the Declaration of Helsinki.

19.2. Guidelines for Good Clinical Practice

The Investigator will ensure that this trial is conducted in accordance with relevant regulations and with Good Clinical Practice.

19.3. Medical Device Regulations

The Investigator will ensure that this trial is conducted in full conformity with:

- European Commission Medical Device Guidelines relating to the application of the EU Directives on Medical Devices
- Guide to European Medical Device Trials and BS EN ISO 14155

19.4. Approvals

Following Sponsor approval the protocol, informed consent form and participant information sheet will be submitted to an appropriate Research Ethics Committee (REC), HRA (where required), regulatory authorities (MHRA in the UK), and host institution(s) for written approval.

The Investigator will submit and, where necessary, obtain approval from the above parties for all substantial amendments to the original approved documents.

19.5. Specific Ethical Considerations for participants in emergency situations

Research in emergency situations is ethically complex because of the urgent nature of the interventions and the often severely compromised capacity of the patient. The processes of enrolment and consent described above, including verbal assent and the involvement of the Advocate represents our attempt to develop a thorough, ethically justified process that both protects patients' rights and interests and enables important research to be done. These processes have been developed in the light of and guided by the provisions laid out in the Mental Capacity Act with special reference to Section 32(9).

19.6. Possible risks/discomfort to participants

Patients referred for emergency cardiac catheterization and PCI will undergo this procedure as would routinely be performed. Patients will therefore be informed of the standard of care procedure and its associated risks. All local protocols will be adhered to and only fully trained staff will carry out procedure according to departmental SOPs.

From a research perspective, the PCI procedure time may be lengthened by around 10 minutes to complete the selected study procedures (OCT acquisitions, angiography derived physiology & aspiration/stent retriever thrombectomy). In the context of a PCI procedure that typically lasts approximately 60 minutes. The additional time should not result in any clinically significant difference to the participants. Very occasionally this additional time can result in some back discomfort for patients having to lie on the angiography bed for the additional time period.

Stent-retriever thrombectomy with the Solitaire X revascularisation device is clinically tested and licensed for endovascular intervention in acute ischaemic strokes. Device failure was reported in one case (0.8%) in the two trials that examined this endpoint with no significant sequelae. Device related complications such as arterial dissection or perforation was reported in 5/211 (2.3%) of ischaemic stroke patients randomised to stent-retriever thrombectomy with the Solitaire X revascularisation device. Perforations and edge dissections are encountered in routine PCI practice in 0.37% and 7.7% of patients and interventional cardiologists are familiar with their management. Coronary perforations and significant

Clinical Trial Protocol Template version 15.0

CONFIDENTIAL

© Copyright: The University of Oxford and Oxford University Hospitals NHS Foundation Trust 2019

Page 47 of 57

Date and version No:22/04/2024 v4.0

dissections are usually treated with a stent which is the treatment these patients will eventually receive for their heart attack.

Finally, stroke in the context of pPCI is reported in 0.25% to 0.5% of STEMI cases and in ~0.8% of STEMI patients with aspiration thrombectomy and PCI. In the Solitaire X device trials, the rate of embolisation to vascular fields proximal to the target vessel is not reported. From a mechanistic perspective, stent-retriever thrombectomy is based on the concept of integration of the stent scaffold into the thrombus which in combination with the withdrawal of the stent into the microcatheter and the continuous aspiration on withdrawal renders embolisation of thrombotic material less likely.

Patients having a heart attack have a higher risk of cardiac mortality, heart failure, periprocedural myocardial infarction and access-site complications (haematoma, bruising, discomfort) by virtue of the underlying condition and its treatment with PCI. Additionally, participants who have suffered a heart attack are frequently re-admitted for a pre-planned procedure to complete revascularisation of their coronary artery disease. We expect that some combination of these events will be noted in trial participants during the study follow-up period. Adverse event reporting will proceed as described in section 13.

